The use of low-dose aspirin during pregnancy has not been associated with a significantly increased risk of hemorrhage during the delivery course, and this dosage would not be expected to result in increased bleeding risk in the postpartum period.

While low-dose aspirin side effects are typically mild, patients may experience some, all, or none of the side effects listed below. Side effects will be assessed at the 4-6 week postpartum visit.

- Mild indigestion
- Nausea
- Vomiting
- Heartburn
- Increased bleeding tendency
- Nosebleeds
- Bleeding gums
- Stomach ulcers
- Wheezing
- Difficulty breathing
- Anaphylaxis

Given the overall minimal side effects associated with the use of low-dose aspirin as well as its routine use during pregnancy in a large subset of patients, identification of risk-mitigating interventions for long-term cardiovascular disease may improve long-term maternal health outcomes.

Low-dose aspirin is considered safe during breastfeeding. After aspirin ingestion, salicylic acid is excreted in breastmilk, with increasing levels detected with increased doses. With low doses of aspirin, defined as 75 to 325 mg daily, aspirin is not excreted in breast milk and salicylate levels are low. Therefore, low-dose aspirin is safe to administer in breastfeeding mothers.

There is also a small risk of loss of confidentiality and risk associated with a blood draw.

Costs to the Subject

- Describe and justify any costs that the subject will incur as a result of participation; ordinarily, subjects should not be expected to pay for research without receiving direct benefit.

There is no anticipated cost to patients.

Data Analysis & Statistical Considerations

- Describe endpoints and power calculations. Provide a detailed description of how study data will be analyzed, including statistical methods used, and how ineligible subjects will be handled and which subjects will be included for analysis. Include planned sample size justification. Provide estimated time

to target accrual and accrual rate. Describe interim analysis including plans to stop accrual during monitoring. Phase I studies, include dose escalation schema and criteria for dose escalation with definition of MTD and DLT.

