Baseline characteristics will be summarized by control and intervention group. Continuous variables will be summarized using mean (standard deviation) or median (25th percentile, 75th percentile) while categorical variables will be summarized using frequency (percentage). Primary outcome, NT-proBNP levels at 4-6 weeks postpartum, will be summarized and compared between groups using two-sample t-test or Wilcoxon rank sum test, depending on the empirical distribution of the data. Secondary outcomes will be compared between groups using the chi-square, Fisher's exact, Mann Whitney U, or student's t-tests, as appropriate. A p-value of M0.05 will be considered significant. Analyses will be performed in R 4.2.0 (R Core Team, 2022) or SAS 9.4 (SAS Institute Inc., Cary, NC).

A prior study at our institution found the following NT-proBNP levels in patients with and without obesity at 4-6 weeks postpartum:

NT-proBNP at 4-6 weeks postpartum	
Mean (SD)	37.4 (32.2)
Median	30.5
Q1, Q3	11.0, 47.0
Range	(2.5-135.0)

Using this mean and standard deviation with a target power of 0.8 at 0.05 level of significance, we calculated a sample size of 90 to detect a medium effect size (Cohen's d = 0.6), which is equivalent to a difference of 19.3 between control and intervention. To account for a 20% drop-out rate, we calculated a sample size of 114 (57 in each group).

This study is designed to be performed within a 24-month timeframe. Patient enrollment will start in spring 2023. Trained research staff will enroll patients in the clinic, on Labor and Delivery and postpartum with the goal to meet our sample size for enrollment by spring 2024.

Data & Safety Monitoring

- Summarize safety concerns, and describe the methods to monitor research subjects and their data to ensure their safety, including who will monitor the data, and the frequency of such monitoring. If a data monitoring committee will be used, describe its operation, including stopping rules and frequency of review, and if it is independent of the sponsor (per 45 CFR 46.111(a) (6)).

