A Data Monitoring Committee (DMC) will be created to perform regular and timely review of data semi-annually in order to identify early, significant benefit or harm for patients while the trial is in progress. Non-identified safety data will be communicated to the DMC who will then meet to review the data. The DMC will be composed of three faculty members within the Duke University Department of Gynecology and Obstetrics. Individuals who are investigators or co-investigators cannot be members. Members must have no financial, scientific, or other conflicts of interest with the study. All investigators understand that the DMC serves as additional human subject's protection, but does not supplant reporting of significant adverse events to the Duke IRB. The DMC may devise its own stopping rules, and if there are significant numbers of adverse events, the DMC will recommend continuation, modification, or termination of the study after each meeting. This recommendation will be communicated to the Principle investigator who is responsible for reviewing the recommendation and forwarding it to the IRB. All investigators understand that the DMC may recommend their own "stopping rule" if other events occur which indicate a significant risk to study subjects.

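### Does giving the DMC a remit to find early benefit put the 5% type I error of the final NT-proBNP test at risk?

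*Combined protocol and SAP*

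**What the plan says.** Under Data & Safety Monitoring, three faculty members who are not investigators on the trial review data every six months "in order to identify early, significant benefit or harm for patients while the trial is in progress". The sentence after that defines the data flow: "Non-identified safety data will be communicated to the DMC who will then meet to review the data". On action, "The DMC may devise its own stopping rules, and if there are significant numbers of adverse events, the DMC will recommend" whether the study continues, is modified or ends. The section closes by saying that the DMC may recommend a stopping rule of its own "if other events occur which indicate a significant risk to study subjects".

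Under Data Analysis & Statistical Considerations, the form's prompt includes "Describe interim analysis including plans to stop accrual during monitoring". The reply gives one between-group comparison of NT-proBNP at 4-6 weeks, by t-test or Wilcoxon test, and a fixed sample size computed "with a target power of 0.8 at 0.05 level of significance". It neither plans an interim efficacy analysis nor says that there is none. Enrolment starts in spring 2023 "with the goal to meet our sample size for enrollment by spring 2024", within a 24-month study.

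**The concern.** A committee told to look for early benefit, and free to devise its own stopping rules, might ask for the primary outcome by arm and act on it. The permission to devise rules is not limited in words to safety. The form asked about interim analysis and the reply does not answer, so no boundary or allocation of alpha is on record.

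Two things would be at stake if that happened. Repeated unadjusted testing would push the overall type I error above 5%. A stop for benefit on a biomarker about halfway through enrolment would also tend to overstate the effect, and would leave roughly half the planned data on bleeding readmissions, transfusions and blood-pressure readmissions.

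**Working it through.** **Step 1: reproduce the plan's sample size.** Inputs from Data Analysis & Statistical Considerations: SD 32.2, d = 0.6, alpha 0.05 (taken as two-sided), power 0.80, drop-out 20%.

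- Difference: 0.6 × 32.2 = 19.32, matching the stated 19.3.
- Two-sided two-sample t-test: 44.59 per arm, rounded up to 45, so 90 in total. Power at 45 per arm is 0.804.
- Drop-out: 45 / 0.8 = 56.25, rounded up to 57 per arm, so 114.

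Both stated figures reproduce. A one-sided test would need only 70, so the plan's figure is two-sided. It contains no allowance for interim looks, as expected of a single-look design.

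**Step 2: what would follow if efficacy were tested at each review.** The plan gives no look schedule, so everything here is assumed: uniform accrual over 12 months, outcome 5 weeks after enrolment, and NT-proBNP tested at 0.05 at each review and again at the end.

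- Information at month 6: (26 − 5) / 52 = 0.404, or about 36 of 90 outcomes (18 per arm), with 57 of 114 enrolled.
- Information at month 12: (52 − 5) / 52 = 0.904.

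The successive z-statistics are jointly normal, with correlation √(t₁/t₂) between looks at information t₁ < t₂. Four million simulated null trials per schedule, with a critical value of 1.96 at every look, give:

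| Assumed interim looks (information) | Two-sided | Interim stop for benefit only |
|---|---|---|
| None | 5.0% | – |
| 0.40 | 8.6% | 6.8% |
| 0.40, 0.90 | 9.7% | 7.4% |
| 0.25, 0.50, 0.75 | 12.6% | 8.8% |
| 0.27, 0.60, 0.94 (accrual over 18 months) | 11.9% | 8.4% |

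The last two rows matter because spring 2024 is a goal, while the 24-month timeframe leaves room for three semi-annual reviews before the end.

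Under the planned effect (d = 0.6), a t-test at 18 per arm would stop for benefit in about 42% of trials. The mean estimate in those trials would be 0.903 SD, that is 0.903 × 32.2 = 29.1 units against 19.3 planned. This comes from a normal model. Against the planning mean of 37.4 it would leave 37.4 − 29.1 = 8.3 units in the aspirin arm. The planning data are skewed (median 30.5, range 2.5 to 135.0), so the figure is only indicative.

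**Step 3: does the plan call for step 2?** Set the statements on monitoring side by side.

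| Element | What the plan says | Points to |
|---|---|---|
| Purpose | benefit or harm | open |
| Data sent | safety data | safety |
| Trigger for a recommendation | adverse events | safety |
| Closing stopping-rule sentence | risk to participants | safety |
| Permission to devise rules | no limit stated | open |
| Primary analysis | one comparison at 0.05, fixed sample size | no interim efficacy test |

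No statement sends NT-proBNP to the DMC, compares it by arm at a review, or tests it before the end. Carried out as written, the plan gives the first row of the error table: 5%.

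**The case for a change.** The strongest case for a change is that the text does name benefit as a purpose, does not confine the DMC's rules to safety, and leaves the form's question on interim analysis unanswered. DMC members stand outside the trial team and must work from the written remit. A rule devised after seeing data could not be shown to be prespecified. A sentence or two would settle the matter at almost no cost.

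The textual observations stand. The inference to a threatened error rate does not. The committee would have to ask for data that the plan does not send it, treat a biomarker as benefit to patients, and test at an unadjusted 0.05. None of these steps is in the document. Benefit or harm to patients can also be read against the clinical events listed under Design & Procedures, such as eclampsia, readmission and transfusion. Some of these could fall within the safety data, so the purpose and the data flow need not conflict.

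The unanswered prompt carries little weight. It is generic form text, and the same paragraph asks for Phase I dose-escalation criteria that do not apply here. A reply that gives one test and a fixed sample size is ordinarily understood to mean that no interim efficacy analysis is planned. A formal boundary, such as p < 0.001 at interim reviews, would hold overall error at about 5.0-5.1%, but it would serve an efficacy look that the plan never proposes.

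**Conclusion.** The concern does not call for a change. Under the natural reading, which is safety-only monitoring, the type I error of the primary test is 5%, and the sample size of 90 evaluable (114 enrolled) stands at 80.4% power. The 7-13% range applies only if NT-proBNP is tested by arm at an unadjusted 0.05 during the trial. It moves with the assumed number, timing and direction of looks, so it measures those assumptions rather than the plan. What remains is a gap in wording that the DMC and the analysts would fill in the ordinary way. A statement that reviews are for safety only, and that NT-proBNP is not compared by arm before the final analysis, would be an optional clarification. Sample size, significance level and final test would all be as they are now.
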